# **List of Abbreviations**

ACSM	American College of Sports Medicine
AE	Adverse Event
BMI	Body Mass Index
СВІ	Center for Biomedical Imaging
CFR	Code of Federal Regulations
CRF	Case Report Form
DM	Diabetes Mellitus
DPN	Diabetic Peripheral Neuropathy
DTI	Diffusion Tensor Imaging
GCP	Good Clinical Practice
HIPAA	Health Insurance Portability and Accountability Act
ICF	Informed Consent Form
ITT	Intention to Treat
IRB	Institutional Review Board
MNSI	Michigan Neuropathy Screening Instrument
MRI	Magnetic Resonance Imaging
MV	Microvascular
MVC	Maximum Voluntary Contraction
NIH	National Institutes of Health
OGTT	Oral Glucose Tolerance Test
OHRP	Office for Human Research Protections
PI	Principal Investigator
RPE	Rate of Perceived Exertion
ROS	Reactive Oxidative Species
SAE	Serious Adverse Event/Serious Adverse Experience
T2DM	Type 2 Diabetes Mellitus
US	United States
VO 2 R	Maximal Graded Exercise Test

# **Protocol Summary**

Title	A cross-over, single-center study investigating the effects of exercise on reversing diabetic peripheral neuropathy
Short Title	Reversing diabetic peripheral neuropathy through exercise
Brief Summary	This project proposes a longitudinal design that uses multinuclear-MRI to evaluate the mechanistic effects of exercise on skeletal muscle function and peripheral nerve integrity in patients with diabetic peripheral neuropathy (DPN), and to determine whether exercise can reverse DPN symptoms. We will prescribe a 10-week exercise program to 40 DPN patients. We will acquire multinuclear-MRI data before and after the intervention that can provide mechanistic insight into the adaptations in lower leg muscle function and peripheral nerve integrity of patients with DPN, and their role in improving DPN symptoms following physical exercise intervention.
Phase	N/A
Objectives	Objective 1: Determine the effect of exercise on peripheral nerve architecture, function, and symptoms of DPN. Objective 2: Determine the effect of exercise on lower leg muscle structure and function in DPN patients.
Methodology	Longitudinal design
Endpoint	Body mass index (BMI), glycosylated hemoglobin (HbA1c), and C-reactive protein will be assessed before and after the 10-week intervention, along with the following measures of neuropathic symptoms: 1) Michigan Neuropathy Screening Instrument (MNSI) symptom questionnaire and the PROMIS physical function and fatigue questionnaire, 2) MNSI physical exam score, 3) Vibration Perception Threshold (VPT) and Calf Muscle performance, 4) Plasma levels hydrogen peroxide as marker of ROS, 5) Lower leg muscle performance (9-item Physical Performance Test), activity monitor with actigraph, and 6) Multinuclear MRI will assess changes in muscle function and peripheral nerve integrity. 7) Utah Early Neuropathy Scale, which is a physical exam specific to early sensory predominant polyneuropathy.
Study Duration	2 years
Participant Duration	~10 weeks
Duration of behavioral intervention	10 weeks
Population	40 patients with Type 2 diabetes and clinical symptoms of DPN (both male and female) between the ages of 40-70 years old
Study Sites	Single-center
Number of participants	40 participants expected to be enrolled across one site
Description of Study Intervention/Procedure	A 10-week exercise program with both aerobic and resistance components, based on the American College of Sports Medicine (2010), will be individually prescribed to 40 DPN patients. Prior to beginning the intervention, subjects will participate in a maximal graded exercise test (VO 2 R) using a cycle ergometer with a metabolic cart and integrated ECG.
Reference Therapy	N/A
Key Procedures	Oral Glucose Tolerance Test (OGTT), multinuclear-MRI, VO 2 R, MNSI, physical therapy, activity monitor

### CONFIDENTIAL

This material is the property of the NYU School of Medicine and Langone Medical Center. Do not disclose or use except as authorized in writing by the study sponsor Drug/Device Template Version: 13 JUN 2016

Statistical Analysis	The analysis will follow the intention-to-treat (ITT) principle and include data from every subject irrespective of whether the subject was compliant with the intervention. A quantitative assessment of compliance with the intervention, ranging from 0 (complete non-compliance) to 1 (full compliance), will be included as a weighting factor to allow more compliant subjects to contribute more to the analysis.
----------------------	---

# 1 Introduction, Background Information, and Scientific Rationale

This document is a protocol for a human research study. This study is to be conducted in accordance with US government research regulations, applicable international standards of Good Clinical Practice, and institutional research policies and procedures.

# 1.1 Background Information and Relevant Literature

Diabetes mellitus (DM) affects 26 million people in the US [1] with 30–50% of Type-2 Diabetes Mellitus (T2DM) patients developing diabetic peripheral neuropathy (DPN) [2-4]. DPN is characterized by impairments of metabolic and microvascular (MV) functions [5], which damage the endoneural capillaries that supply the peripheral nerves [6]. Prolonged DPN can lead to local ischemic conditions in the lower extremities, causing loss of peripheral nerve integrity, neurogenic muscle atrophy, fatty infiltration [7, 8], and loss of muscle endurance [9-12]. These synergistically contribute to altered gait, impaired balance, and increased fall risk, which can lead to bone fractures, poorly healing wounds, and chronic infections [13-15] that often require an amputation [16, 17]. There are no therapies to prevent or reverse the progress of DPN [18-20]. Therefore, it is very important to establish effective treatments for DPN.

A growing body of literature supports the benefits of combining moderate-intensity aerobic exercise with resistance training to improve glycemic control and insulin sensitivity in individuals with DM [21, 22]. However, little is known about the benefits of exercise in individuals with DPN. Preliminary single-group studies conducted by [name] (co-investigator) have shown that a moderate intensity supervised exercise significantly improve their cardiorespiratory function, and can also improve DPN symptoms, including nerve function and cutaneous innervation (Fig. 1) [23, 24]. In addition, exercise can improve vascular endothelial function in DPN [25]. Non-invasive exercise intervention is particularly valuable in this population due to its safety, low cost, and potential to augment pharmacological interventions. Our longitudinal study design seeks to understand the effects of exercise in skeletal muscle function and peripheral nerve integrity of DPN patients. We hypothesize that exercise can partially reverse DPN progression because it promotes MV dilation, reduces oxidative stress, and increases the abundance of neurotrophic factors, all of which are compromised in DPN [26]. Exercise will be able to improve lower limb muscle function by inhibiting key metabolic pathways that cause hypoxia. Successful completion of our study will facilitate the development of mechanism-based intervention strategies for individuals with DPN.

intervention.

# 1.2 Rationale

Hyperglycemia is an important factor in the development of DPN. However, the pathophysiological processes through which hyperglycemia causes DPN are not fully understood. Furthermore, large clinical studies (ACCORD [27], ADVANCE [28], VADT [29]) have shown that good glucose control is insufficient to reduce the occurrence of foot complications, including DPN and diabetic foot ulcers. There are no Food and Drug Administration (FDA)-approved treatment options that target the underlying pathogenesis of DPN [19, 30]. Therefore, it is important to establish strategies to delay or reverse the effects of DPN.

We hypothesize that DPN patients who undergo 10 weeks of exercise will show improved peripheral nerve integrity and function, and that exercise will improve the structure, local metabolic, and MV functions of skeletal muscle. A major obstacle to assessing how DPN affects skeletal muscle and peripheral nerves is the lack of sensitive, objective, and reproducible tests to detect small changes in muscle and nerve functions [10]. Multinuclear-MRI can bring new insights into how DPN affects skeletal muscle (31P)-MRI techniques that can reliably assess skeletal muscle metabolic function [34, 35], as well as rapid

CONFIDENTIAL

This material is the property of the NYU School of Medicine and Langone Medical Center. Do not disclose or use except as authorized in writing by the study sponsor

techniques to quantify blood oxygenation level dependent (BOLD)-MRI signals, sensitive to MV function [36-38] and its adaptations after exercise interventions [39]. In addition, we will use diffusion tensor imaging (DTI), a powerful MRI technique, to quantitatively assess neuronal integrity and detect nerve injury and monitor reinnervation [40-46]. The use of DTI will allow us to non-invasively assess peripheral nerve adaptations after exercise intervention. Finally, we will use IDEAL-MRI to quantify levels of intramuscular adipose tissue (IMAT), which are elevated in DPN [47-50]. We will prescribe a 10-week exercise program, with both aerobic and resistance components [14, 24], to 40 DPN patients who will receive personal supervision from health professionals. We will acquire multinuclear-MRI data at three time points: 1) baseline, 2) pre-intervention and 3) post-intervention. We will measure plasma levels of reactive oxidative species (ROS) as markers of oxidative stress.

Like all longitudinal studies, exercise intervention studies are at risk of losing participants who choose to discontinue their participation during the intervention. Our team has developed effective strategies to promote high levels of adherence even with this challenging population, with our preliminary studies showing low attrition rates [23, 24]. Our previous experience with intervention studies indicates that the main reason patients discontinue participation is the cost associated with travel (bridge/tunnel tolls, parking, bus, and taxi fare). Therefore, we have budgeted funds to offset transportation expenses for participants (up to \$20 per visit). To further convenience our participants, we will offer flexible scheduling for appointments in our research dedicated physical therapy center ([name]), including availability 5-days/week and 12-hrs/day (from 8am to 8pm). In the current proposal, data analysis will follow the ITT principle and include data from every subject regardless of whether the subject complied with the intervention.

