# 9.3 Description of Statistical Methods

A weighted paired sample *t*-test will be used to assess whether each outcome changed from baseline to follow-up as a result of the exercise intervention. Weighted analysis of covariance (ANCOVA) will be used to compare the time points in terms of the change in each outcome. The change in each outcome from baseline to follow-up will be the dependent variable and the ANCOVA model will include the matching factors (age, baseline MNSI) and the measure of general activity level as numeric covariates and the binary indicator of intervention as a classification factor. The secondary objective is to assess the extent to which exercise induced improvements in DTI outcomes are mediated or explained by reduction in ROS. After testing the effect of the intervention on the change in DTI and the correlation between changes in DTI and ROS, an incomplete causal pathway meditational analysis will be conducted using the method of Baron and Kenny[63] with a bootstrap based test of the indirect (mediation) effect of ROS. The exploratory objective to identify baseline factors (e.g., age, MNSI, general activity) predictive of improvement, represented as the baseline to follow-up change in each outcome, will be addressed using linear regression and bivariate correlations. This analysis will be stratified by intervention and then conducted using data from both intervention groups combined. In each case, the assessment of compliance will be included as a weighting factor.

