# 9.3.2 Analysis of the Primary Efficacy Endpoint(s)

A matched-pairs Wilcoxon signed rank test will be applied to the within-subject change in each outcome among subjects demonstrating full compliance with the exercise program. Additionally, weighted analysis of covariance (ANCOVA) will be used to test the change in each outcome adjusting for the measured level of compliance using data from all subjects. The values of each outcome at

CONFIDENTIAL

baseline and follow-up for all subjects will be the dependent variable and the ANCOVA model will include time (baseline versus follow-up) as the within-subject factor of interest covariates, the measure of compliance as numeric covariate and an anonymized subject ID as a classification factor so that the comparison of times will be based on their within-subject difference. The secondary objective is to assess the extent to which exercise induced improvements in DTI outcomes are can be at least partially explained by reduction in ROS will be addressed using linear regression, The baseline to follow-up change in each outcome will be the dependent variable and the model will include the measure of compliance as a numeric factor and the within-subject change in ROS as the numeric factor of interest. A second regression will be conducted with baseline factors (e.g., age, MNSI, general activity) added to the model in order to identify factors predictive of improvement in each outcome.

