## 9.4 Sample Size

Assessment of statistical power was based on tests conducted at the two-sided 5% significance level and the preliminary data in Table 3. Under the conservative assumption of a moderate within-subject correlation ( $\rho$ =0.5) between baseline and follow-up measures, the expected mean and SD of the within-subject change in the outcomes is given in Table 4. It is noted that statistical power will be higher if  $\rho$ >0.5 as observed in

Table 3. The mean and standard deviation (SD) of the BOLD response, PCr resynthesis rate and

MNSI score before (baseline) and after (follow-up) a control or exercise intervention observed in

the majority of longitudinal imaging studies. With data from 40 subjects included in the analysis according to the

		Ex	er
	Baseline		
Outcome	Mean	SD	T
BOLD respone	3.24	1.04	14
PCr resynthesis	41.16	14.1	~
MNSI	5.2	1.4	- Ta

ITT principal the study will have 80% power to detect a mean within-subject change in each outcome among subjects in each intervention group provided the change is between 10% and 18% when expressed as a percentage of the mean at baseline. The mean percentage change observed in the preliminary data among subjects

preliminary data.

 xercise
 Control

 Follow-up
 Baseline
 Follow-up

 Table 4. Expected mean and standard deviation (SD) of the within-subject change in BOLD response, PCr resynthesis rate, and MNSI score from baseline to after a control or exercise intervention based on the preliminary data in Table 3 and the conservative assumption of moderate within-subject correlation (p=0.5) between baseline and follow-up measures.

	Exer	cise	Control		
Outcome	Mean	SD	Mean	SD	
BOLD respone	1.11	1.26	0.18	1.42	
PCr resynthesis	10.61	12.85	0.06	8.53	
MNSI	1.20	1.78	NÁ		

CONFIDENTIAL

This material is the property of the NYU School of Medicine and Langone Medical Center. Do not disclose or use except as authorized in writing by the study sponsor

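### Analysis is promised for every subject, but each named test of the exercise change learns only from complete before-and-after pairs, and no method for missing outcomes is given

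*Combined protocol and SAP*

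**What the plan says.** Section 1.2 names loss of participants as a risk of the design, describes retention measures, and ends that paragraph by saying the ITT analysis will "include data from every subject regardless of whether the subject complied with the intervention". The Statistical Analysis row of the Protocol Summary says the analysis will "include data from every subject irrespective of whether the subject was compliant with the intervention", and section 9.3.4 repeats this.

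Section 9.4 sets the test level ("Assessment of statistical power was based on tests conducted at the two-sided 5% significance level") and bases its 80% power on all those enrolled: "With data from 40 subjects included in the analysis according to the" ITT principle, "the study will have 80% power to detect a mean within-subject change in each outcome". Section 4.6 ends recruitment at about 40.

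The tests named for the change are:

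- Section 9.3: a weighted paired t-test.
- Section 9.3: a weighted ANCOVA comparing exercise with control, in which "The change in each outcome from baseline to follow-up will be the dependent variable".
- Section 9.3.2: "A matched-pairs Wilcoxon signed rank test will be applied to the within-subject change in each outcome", in full compliers only.
- Section 9.3.2: a weighted ANCOVA on the baseline and follow-up values of all subjects, with "an anonymized subject ID as a classification factor", so that time points are compared within subject.

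The documents give no imputation rule, likelihood-based model or sensitivity analysis for missing outcomes. What they do provide is retention effort, an invitation to endpoint testing after withdrawal (sections 4.7.2 and 6.4.5, MRI included), and an instruction in section 10 to explain missing CRF data.

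**The concern.** Because the plan names its estimators, their treatment of an incomplete record follows from their form. Three of the four need two values to form a change. The fourth accepts a single value, but its subject term absorbs that value completely. A participant measured before exercise and not after therefore has no influence on the estimated exercise change, although the plan reads as if all 40 contribute.

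The stake is bias more than precision. If those lost differ in their pre-exercise values, regression to the mean makes the average change among the remaining participants differ from the average change for all 40. The pre-exercise values that could correct this have been collected, but the named tests do not use them for that purpose.

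**Working it through.** **1. Reproduce the plan's figure.** Detectable change as a percentage of the baseline mean = (z₀.₉₇₅ + z₀.₈₀) × SD of change / √n / baseline mean, with 1.960 + 0.842 = 2.802, n = 40, Table 4 SDs and Table 3 baseline means.

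- BOLD: 2.802 × 1.26 / 6.325 / 3.24 = 17.2% (exact t 17.7%)
- PCr: 2.802 × 12.85 / 6.325 / 41.16 = 13.8% (exact t 14.2%)
- MNSI: 2.802 × 1.78 / 6.325 / 5.2 = 15.2% (exact t 15.5%)

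All three lie inside the stated 10% to 18%, and the upper end reproduces. The calculation uses 40 complete pairs, which is everyone enrolled.

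**2. Effect of loss on power.** The documents mention low attrition but give no rate, so 10%, 20% and 30% are assumed. That leaves 36, 32 and 28 pairs. Detectable changes (exact t) become 18.7, 19.9 and 21.4% for BOLD, 15.0, 16.0 and 17.1% for PCr, and 16.4, 17.5 and 18.8% for MNSI. Even with 28 pairs, power for the anticipated changes is 99.4% (BOLD), 98.8% (PCr) and 93.0% (MNSI).

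**3. The ANCOVA with subject ID.** A subject with one value is fitted exactly by their own intercept and leaves no residual. In simulated data with 8 of 40 lacking follow-up, the time effect was 1.0140 (SE 0.1748, 31 df), identical to the fit on pairs alone. Adding 100 to those eight baselines changed nothing. A random-intercept model on the same data did use them (0.998, SE 0.170).

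**4. The exercise-versus-control ANCOVA.** With three scans, the same eight subjects keep a control-phase change: 72 rows (40 + 32) rather than 64, and SE 0.267 rather than 0.276 (simplified to the phase indicator, unweighted). The extra rows do not remove the bias. In a simulation with equal variances and 20% loss, the phase contrast was biased by -0.067 or -0.113 SD, essentially the same as the complete-pair change (-0.067 or -0.110). MNSI (Weeks 0, 1 and 18 in Attachment A) and bloodwork (Weeks 1 and 18) have no Week 5 value, so a subject missing Week 18 supplies no change of either kind.

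**5. Size of the bias.** Assume the log-odds of missing the post-exercise value fall by ln 2 or ln 4 per SD of the pre-exercise value, with 20% loss overall. Numerical integration gives a mean pre-exercise value among those kept of k = 0.129 or 0.216 SD above the full group. Bias of the complete-pair change = k × s₁ × (ρ s₂/s₁ − 1), with ρ = 0.5 from section 9.4, s₁ the baseline SD from Table 3, and s₂ solved from SD²(change) = s₁² + s₂² − 2ρ s₁s₂. The larger root is used for PCr, because the follow-up SDs are not legible in the extracted table.

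| Outcome | s₁ | s₂ | Slope | Bias, odds ×2 | Bias, odds ×4 |
|---|---|---|---|---|---|
| BOLD | 1.04 | 1.40 | -0.326 | 0.129 × 1.04 × -0.326 = -0.044 (3.9% of 1.11) | -0.073 (6.6%) |
| MNSI | 1.4 | 2.00 | -0.285 | 0.129 × 1.4 × -0.285 = -0.051 (4.3% of 1.20) | -0.086 (7.2%) |
| PCr | 14.1 | 11.05 | -0.608 | 0.129 × 14.1 × -0.608 = -1.11 (10.4% of 10.61) | -1.85 (17.5%) |

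Simulations at n = 40 give about 3 to 7% for BOLD, 5 to 7% for MNSI and 10 to 18% for PCr, which agrees within simulation error. The likelihood-based estimate has bias of about 0 throughout. The sign of the bias depends on who leaves.

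**6. If loss is unrelated to the outcome.** There is no bias. The gain is a standard error about 3% smaller (0.172 against 0.177 SD at 20% loss, equal variances).

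**The case against.** Several points on the other side are sound.

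- The inclusion sentences concern compliance. They promise to keep non-compliers, not to analyse people without an outcome. A non-complier who attends endpoint testing has a pair, and withdrawers are invited to attend. This stands. The plan does not break an express undertaking about missing outcomes; it gives no method for them.
- A reader might infer that anyone missing follow-up is deleted and all their scans are thrown away. The documents do not support that. No deletion rule is stated, and under a three-scan schedule the Week 1 and Week 5 scans still give a control-phase change.
- Section 9.3.2 calls subject ID a classification factor and does not say that its effect is fixed. A random effect would recover some information. However, the stated purpose, a comparison based on differences within subject, points to the fixed reading.
- Section 1.2 gives travel cost as the main past reason for stopping, with funds budgeted to offset it. If that drives loss, it may be unrelated to the change and the complete-pair mean is unbiased. No passage shows that people with worse nerve or muscle status leave. On the other hand, section 4.7.1 lets the investigator end participation for adverse events or laboratory abnormalities, so outcome-related loss cannot be ruled out.
- The bias figures are for an unweighted mean without covariates, whereas the section 9.3 tests are weighted by compliance and the ANCOVA adjusts for age, baseline MNSI and activity. The figures are illustrations, not predictions for the planned models.

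**Conclusion.** The point holds for the exercise change. All the named tests of that change use complete pairs only, the power statement counts 40 such pairs, and nothing is said about missing outcomes. For MRI the loss of information is partial if three scans are taken; for MNSI and blood outcomes it is complete for anyone without Week 18 data.

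The consequence is a possible bias that is modest for BOLD and MNSI and larger for PCr, as in the table. It rests on an assumed 20% loss, an assumed dependence on the pre-exercise value, ρ = 0.5 and the Table 4 SDs. It vanishes if loss is unrelated to the change. A reader might also infer that the study is underpowered once dropouts are counted, but step 2 shows otherwise for the anticipated pre/post changes. This is a change that should be made, not a flaw that invalidates the design.

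**What to change.** In sections 9.3 and 9.3.2, make the main analysis of each outcome a likelihood-based repeated-measures mixed model, with visit as a categorical effect and the within-subject covariance modelled. Use every observed value at the visits where Attachment A collects that outcome:

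- MRI: Weeks 1, 5 and 18
- MNSI and bloodwork: baseline and Week 18 (MNSI is listed in both Weeks 0 and 1, so state which is baseline)
- Calf performance and PROMIS: Weeks 7 and 16
- Height and weight: Weeks 1, 6 and 17

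For MRI, define the exercise change as Week 18 minus Week 5, and the phase contrast as (Week 18 − Week 5) − (Week 5 − Week 1). First reconcile sections 9.3.1 and 12.3, which give two scans, with sections 1.2 and 3.1 and Attachment A, which give three. With two scans the phase contrast cannot be estimated.

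State how the section 9.3 covariates and the compliance weighting carry over to the model. Report the number observed at each visit, and keep the complete-pair tests as sensitivity analyses.

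The cost is SAP wording and a standard model, with no new data. The price is reliance on a missing-at-random assumption, which should be stated.
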